12. DATA AND SAFETY MONITORING PLAN

All of the materials collected are for research purposes only, and data will be kept in strict confidence. No information will be given to anyone without permission from the subject. Confidentiality will be ensured by use of unique identification codes. All data, whether generated in the laboratory or at the bedside, will be identified with a randomly generated identification code unique to the subject.

In the course of conducting the questionnaires, we may learn about mental illness symptoms including suicidal ideation and/or intent, or other risks of harm. A research emergency protocol will be followed to detect, assess, and refer/triage persons to the most appropriate existing, non-research crisis resource available to them. In addition, the PI will be responsible for internal data monitoring on a scheduled basis including review of protocol deviations, adverse events, unanticipated problems, eligibility/screening and the informed consent process. Finally, the project team will meet regularly to assure that all confidentiality procedures are being maintained.

Data security will be maintained by limiting access to the minimum number of research team members required to complete the aims. A secure computer folder and password protected files, maintained on a secure server, will be used to store data. Data will be accessed any time a new participant enrolls or completes an assessment and we will ensure no identifying information is linked to answers. No identifiable data will be published or disclosed to third parties. At the end of the study, identifying information will be destroyed. Data collected from interviews and surveys will be stored until after all publications are completed.

The research team will be thoroughly trained on the research protocol and procedures. A Manual of Procedures will be developed for project staff to reference. Protocol deviations/violations and Unanticipated Adverse Events will be communicated to the IRB per HFHS IRB policy by the Project Coordinator or PI and again reported at continuing review. The Project Coordinator will maintain records of approved protocol, initial IRB submission, and approved materials and tracking system and will make amendments to protocol/materials for approval by IRB when warranted.

Unanticipated Problems and Adverse Events

If applicable, describe process for reporting any unanticipated problems and adverse events to the IRB

Adverse Events (AEs) are any untoward or unfavorable occurrence in a study participant, including any abnormal signs, symptoms, or disease, temporally associated with the participants' involvement in the research, whether or not considered related to participation in the research. Serious Adverse Events (SAEs) include any adverse event that results in death, is life threatening, or places the participant at immediate risk of death from the event as it occurred, requires or prolongs hospitalization, causes persistent or significant disability or incapacity, results in congenital anomalies or birth defects, or is another condition which investigators judge to represent significant hazards. Unanticipated Problems (UPs) are defined as any incident, experience, or outcome that is unexpected (in nature, severity, or frequency), related

or possible related to participation in the research, and suggests that the research places participants or others at a greater risk of harm (including physical, psychological, economic, or social harm) than was previously known or recognized.

For reporting of AEs and SAEs, the interventionist or other member of the research team will immediately notify a principal investigator. The investigator ([name] or [name]) will determine how to classify the event. AEs or SAEs will be classified according to severity, expectedness, and potential relatedness to the study intervention. Severity classifications will be: mild, moderate, or severe. Classification will be informed by the severity of the event and the degree of inconvenience or interruption of the participant's daily activities. Expectedness classifications will be: unexpected or expected. Unexpected classification will occur when the nature or severity of the event is not consistent with the information about the individual, the population, or the intervention. Relatedness classifications will be: definitely related, probably related, possibly related, or not related. Classification will be informed by temporal sequence and known/expected response patterns.

FOREward Together: Training Peer Recovery Coaches to Promote Retention and Adherence to
MOUD

NCT05098795

Approved Statistical Analysis Plan

Approved 7/31/2024

Data Analytic Plan

Primary Outcomes: MOUD treatment retention and feasibility of intervention delivery.

Descriptive statistics will be used to characterize the sample. MOUD retention was defined *a priori* as return visits, measured for up to 24 weeks. We will calculate the percentage of participants still enrolled in the program over this period of time. Feasibility was defined, *a priori*, as the percent of patients who agreed to participate in the intervention. We will calculate the proportion of individuals who were screened eligible to the percent that engaged in the intervention, measured at study completion.

Secondary Outcomes: Intervention acceptability and intervention fidelity

Descriptive statistics will be examined for all secondary outcomes. Intervention acceptability was defined *a priori* as the percentage of patients enrolled who attend at least 75% of scheduled sessions. Intervention fidelity was defined *a priori* as the percentage of intervention elements delivered as intended. Following fidelity coding, we will calculate the number of accurately delivered components relative to the total number of coded components among a random selection of 20% of sessions.

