After discussing the study with the research team member by telecommunication (audio or video) or in-person and based on continued interest, the participant will be invited to complete the informed consent process (detailed below in Procedures) and to schedule the baseline assessment. In all cases, patients will be informed that the study provides ClinCard compensation for participation (see Recruitment Script). The study team member will reiterate that participation in the study will in no way affect any services that they receive at DRP or elsewhere and will emphasize that they may participate through tele-sessions if this would work best for them or due to COVID-19 safety concerns. The study team member will also work with the participant to understand their access to technology for study communication. The study team will work with each participant to try to accommodate their individual frequency needs (aiming for a minimum of every other week) for intervention and other study-related contact, with flexibility of timing based on each individual's treatment schedule and needs. The study team will keep a record of participant access to technology (e.g. phone minutes, texting capability, video capability, WiFi, etc.) in a HFHS REDCap database (non-identifiable information only). As needed, the research team will provide information on/assistance with applying for a phone through public assistance programs and other resources available at DRP.

a. Eligibility Criteria:

Participants must (1) meet criteria for SUD; and (2) be over the age of 18.

Exclusion criteria will be (1) demonstrating active, unstable or untreated psychiatric symptoms, including mania and/or psychosis; or (2) inability to understand the study and give informed consent in English.

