Following completion of the baseline assessment, the participant can meet with the PRC approximately 8 BA sessions that can be scheduled based on individual treatment plans and particular participant needs, with the aim of a minimum session frequency of every other week. Following treatment completion, participants will be able to schedule up to 4 booster sessions to provide further assistance with addressing barriers to treatment. These sessions will be held either remotely or in-person at the drug treatment center, depending on participant availability and preference. Based on participant needs and preferences, the PRC may provide a second check-in between BA sessions. The additional check-in will focus on challenges and barriers that participants are experiencing in their SU treatment. These sessions can be conducted via phone (including telephone, Zoomvideoconference (Zoom), or in-person at the drug treatment center. Participants can conduct remote sessions from their homes or other preferred private locations. In-person sessions will take place at DRP or other mutually convenient locations and follow all necessary COVID-19 precautions outlined in the approved in-person human subjects research proposal. Participants may also choose to participate in these virtual sessions at DRP during routine visits to the treatment center with the peer at a separate location. These procedures will follow the current telehealth practices and protocols being used at DRP.

The study interventionist will be a trained and supervised PRC who will receive training in protocol and intervention procedures. Supervision sessions between the PRC and DRP clinical supervision staff will take place approximately weekly, with inclusion of key personnel as needed (I.e. Drs. [name], [name] and/or [name]). The supervisor will utilize recordings of intervention sessions while supervising the PRS. The peer hired as the study interventionist will be a Michigan Certified Peer Recovery Specialist (CPRS). CPRS certification is managed by Michigan Department of Health and requires 56 hours of training.

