within approximately one week. Because this interview will ask about the participants' experiences with the PRC, the interview will be conducted by a trained member of the study staff and the participants' responses will not be shared with the PRC. The participant will be asked for their consent for the interview to be recorded. They will be assured that audio recording will be used for research purposes only. The recording will be uploaded to UMB's Box folder immediately following the session, and the audio file will be deleted from the recording device.

It will take approximately 30-60 minutes to complete the baseline assessment, approximately 15-30 minutes to complete the midpoint assessment, approximately 30-60 minutes to complete the posttreatment assessment, and approximately 30 minutes to complete the posttreatment exit interview. All compensation for study related activities will be in the form of a reloadable ClinCard. The participant will receive \$10 (ClinCard) for completing the baseline, \$15 for completing the midpoint assessment, a \$25 ClinCard for completing the posttreatment assessment, and \$25 for completing the exit interview. Total compensation for baseline assessment, midpoint assessment, posttreatment assessment, and exit interview will be up to \$75.

We recognize that meeting with participants remotely or in person may both present new challenges to participation, including cost associated with using their own device for session contact or cost of attending sessions when not scheduled for other services at DRP. We also understand that participants may also face additional transportation costs when presenting in-person to the drug treatment center during COVID-19. As such, participants will receive compensation in the form of ClinCards for each session attended to cover transportation and/or telecommunication costs. \$10-25 per session will be provided to participants after each session attended for the duration of the study. We have chosen to incrementally increase compensation as sessions persist in order to encourage long-term retention. Participants will receive \$10 per session for BA 1-2, \$15 per session for BA 3-4, \$20 per session for BA 5-7, and \$25 for BA 8. Total compensation for intervention session attendance (above the compensation for assessment participation) will have a maximum of \$135, reflecting attendance of the 8 sessions.

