During trial assessments or BA sessions, it is possible that information may be disclosed about childhood abuse and neglect experiences and/or alleged perpetrators of abuse. We are aware of our obligation to report, and will follow the State of Michigan's mandatory child maltreatment reporting laws to the extent that reporting does not violate any applicable federal rules or policies. For this study, we state explicitly our responsibility to report in the body of the consent form.

There is a slight risk of potential for coercion (compensation). Compensation is linked to completion of research assessments as well as attendance of intervention sessions. Participants will be paid \$10 for the baseline assessment and intervention sessions 1-2, \$15 for intervention sessions 3-4 and the midpoint assessment, \$20 intervention sessions 5-7, and \$25 for intervention session 8, the post-treatment assessment and exit interview. The maximum compensation for this study accumulates to \$260 with all sessions, assessments, and the exit interview completed. This compensation is modest and reasonable for the tasks being requested and are consistent with other clinical intervention research trials.

Other risks: One risk in this study related to SUD and its treatment is the stress of and symptoms associated with withdrawal; these will be monitored and treated by the participant's treatment team at the DRP and any worsening of these identified by the study team or study interventionists will be reported to the DRP.

Throughout the study, the PIs and members of the research team will ensure strict adherence to study procedures according to the IRB-approved protocol. Should there be any protocol deviations or unanticipated problems, a PI will notify the HFHS IRB.

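### Does the acceptability outcome need a written definition of which sessions count as scheduled?

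*SAP*

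**What the plan says.** The SAP (Data Analytic Plan, Secondary Outcomes) defines acceptability "as the percentage of patients enrolled who attend at least 75% of scheduled sessions". It says this was fixed a priori and that all secondary outcomes are handled descriptively. The person-level denominator is stated: everyone enrolled. The session-level denominator is the single word scheduled.

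The protocol has four pieces of text that bear on that word.

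- **The course.** Section 3 (Intervention and Assessments) offers "approximately 8 BA sessions that can be scheduled based on individual treatment plans and particular participant needs".
- **Flexibility.** Section 2 says "The study team will work with each participant to try to accommodate their individual frequency needs", aiming for contact at least every other week.
- **Extras.** Section 3 adds "Following treatment completion, participants will be able to schedule up to 4 booster sessions", and says that, depending on need, "the PRC may provide a second check-in between BA sessions".
- **Payment.** Section 3 says "participants will receive compensation in the form of ClinCards for each session attended". It sets a rate for each of BA 1 to BA 8 and caps the session total at $135, "reflecting attendance of the 8 sessions". Sections 4 and 6 repeat the numbering, ending with the payment "for intervention session 8, the post-treatment assessment and exit interview".

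**The concern.** Section 3 uses the verb schedule for sessions arranged to suit each person, so a reader could take the SAP's scheduled sessions to mean appointments booked. On that reading the denominator stops growing when a participant leaves. Someone who attends two sessions, has no third one booked and then disappears has kept all appointments and counts as finding the intervention acceptable. Someone who enrols and never has a session booked is 0/0.

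The two readings answer different questions. One asks whether participants received most of the intervention; the other asks whether they kept the appointments made. Acceptability is one of the pilot's stated aims, and section 2 describes a population that struggles with retention, so early leavers are to be expected. If the denominator were chosen after the data were seen, the more flattering figure could be reported.

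**Working it through.** **Inputs.** Threshold 75% (SAP, Secondary Outcomes). Nominal course of 8 BA sessions, up to 4 boosters, and pay rates (protocol section 3). Maximum enrolment 40 (protocol section 2). The documents give no expected or target value for acceptability, so there is none to reproduce.

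**Check that the course is eight.** The session pay schedule is 2 × $10 + 2 × $15 + 3 × $20 + 1 × $25 = $135. This matches the stated cap, so the cap corresponds to exactly eight sessions.

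**Rule on the planned course.** 0.75 × 8 = 6, so a participant meets the criterion with 6 or more attended. Nothing booked is 0/8 = 0%, a clear fail, so the 0/0 case does not arise.

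**Rule on booked sessions.** The number needed is 0.75 × booked, rounded up:

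| Booked | 1 | 2 | 3 | 4 | 5 | 6 | 7 | 8 |
|---|---|---|---|---|---|---|---|---|
| Attended, needed | 1 | 2 | 3 | 3 | 4 | 5 | 6 | 6 |

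**Where the rules disagree, up to 8 booked.** There are eight attended/booked patterns: 1/1, 2/2, 3/3, 3/4, 4/4, 4/5, 5/5 and 5/6. Each passes on bookings (75% to 100%) and fails on eight (1/8 = 12.5% to 5/8 = 62.5%). With 7 or 8 booked, both rules need 6 and agree.

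**Sensitivity to one missed booking.** The 2-of-2 case needs no third session to have been booked and missed. With one such miss it becomes 2/3 = 66.7% and fails on both rules. The patterns 3/4, 4/5 and 5/6 already include one miss and still pass on bookings.

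**More than 8 booked.** Section 3 has the coach keep following up after missed sessions, so rebooking can take the count past eight. Then 6/9 = 66.7% and 8/11 = 72.7% fail on bookings and pass on eight. The booked reading can therefore lower the figure as well as raise it.

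**Boosters.** If the 4 boosters joined the denominator, a participant who completed the whole course and took none would score 8/12 = 66.7% and fail. Section 3 places boosters after treatment completion, so they are not naturally part of the course being scored.

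**Size.** Each participant classified differently moves the result by 1/40 = 2.5 points. The documents do not say how many there will be. As an assumption for scale only, suppose 5, 10 or 20 of 40 leave after 2 of 2 and everyone else attends 8 of 8. Bookings give 40/40 = 100% each time. The planned course gives 35/40 = 87.5%, 30/40 = 75% and 20/40 = 50%.

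**The case for a change.** The best case for a change is that the gap is real, cheap to close and not trivial if many participants leave early. Scheduled is the word the protocol uses for individually arranged sessions, the payment text was written to set payments rather than to define an outcome, and the protocol says approximately eight. The primary retention outcome does not fully cover the gap either, because a participant can stop BA sessions and remain enrolled at the centre.

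Much of this stands: neither document ties a session count to acceptability, and the eight-pattern enumeration is correct. Three things weaken it.

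- In section 3 the approximately eight sessions are the set being scheduled. What sections 2 and 3 individualise is mainly frequency and timing. Neither describes an agreed plan of fewer than eight; only the word approximately leaves room for one.
- Attendance is documented and paid session by session, so a count against eight can be made for every participant. The supplied text names no record of bookings, which the other reading would need. The Measures document and Manual of Procedures were not supplied and might contain one.
- A consistent upward bias is not shown, since rebooked sessions push the other way.

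The payment text is not flawless. The $260 overall maximum in sections 4 and 6 exceeds $135 for sessions plus $75 for assessments and interview, which is $210. But both sections still list the intervention sessions as 1 to 8, so the course length does not depend on that total.

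**Conclusion.** No change to the plan is needed. The definition leaves one word open, and the protocol gives an analyst a clear way to fill it: eight BA sessions, at least six attended, all enrolled participants in the denominator, boosters and between-session check-ins outside the course. Under that reading an early leaver with 2 of 2 counts as 25% and does not meet the criterion. No rule stated in either document is shown to give a wrong result.

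The consequence is limited. Acceptability here is one descriptive secondary outcome in an open-label pilot of at most 40, with no benchmark, test or decision rule, so no error rate, power or sample size depends on it. Programme retention is reported separately as a primary outcome, and the feasibility and acceptability questionnaire and the exit interviews do not use this denominator.

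The conclusion assumes that the eight numbered sessions are the course the SAP had in mind. The documents support this without stating it. If booked sessions were intended, the result could differ by 2.5 points per affected participant, in either direction, and the number affected cannot be derived from the documents.
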